2.3 Response Assessment

2.3.1 Evaluation of Best Overall Response

The best overall response is the best response recorded from the start of the study treatment until disease progression or the last response recorded, taking into account any requirement for confirmation and censoring rules regarding subsequent therapy. The patient's best overall response assignment will depend on the findings of both target and non-target disease and will also take into consideration the appearance of new lesions. Furthermore, depending on the nature of the study and the protocol requirements, it may also require confirmatory measurement.

2.3.2 Time Point Response

At each protocol specified time point, a response assessment occurs. Table 2.3.2-1 provides a summary of the overall response status calculation at each time point for patients who have measurable disease at baseline. When patients have non-measurable (therefore non-target) disease only, Table 2.3.2-2 is to be used.

Table 2.3.2-1: Time Point Response: Patients With Target (\pm Non-Target) Disease

Target Lesions	Non-Target Lesions	New Lesions	Overall Response
CR	CR	No	CR
CR	Non-CR/non-PD	No	PR
CR	Not evaluated	No	PR
PR	Non-PD or not all evaluated	No	PR
SD	Non-PD or not all evaluated	No	SD
Not all evaluated	Non-PD	No	NE
PD	Any	Yes or No	PD
Any	PD	Yes or No	PD
Any	Any	Yes	PD

CR = complete response, PR = partial response, SD = stable disease, PD = progressive disease and NE = inevaluable

Table 2.3.2-2: Time Point Response: Patients with Non-target Disease Only

Non-Target Lesions	New Lesions	Overall Response
CR	No	CR
Non-CR/non-PD	No	Non-CR/non-PD ^a
Not all evaluated	No	NE
Unequivocal PD	Yes or No	PD

Table 2.3.2-2: Time Point Response: Patients with Non-target Disease Only

Non-Target Lesions	New Lesions	Overall Response
Any	Yes	PD
CR = complete response, PD = progressive disease and NE = inevaluable		

^a Non-CR/non-PD is preferred over SD for non-target disease since SD is increasingly used as endpoint for assessment of efficacy in some trials so to assign this category when no lesions can be measured is not advised.

2.3.3 Best Overall Response

Best response determination of complete or partial response requires confirmation: Complete or partial responses may be claimed only if the criteria for each are met at a subsequent time point of ≥ 4 weeks (28 days) later. In this circumstance, the best overall response can be interpreted as in Table 2.3.3-1. When SD is believed to be best response, it must meet the protocol specified minimum time from the date of first treatment or randomization date.

For example, if the first scheduled follow-up imaging visit is Week 6 (± 7 days) for a particular protocol, a Best Response of SD can only be made after the subject is on-study for a minimum of 6 weeks (42 days) minus 7 days, for an absolute minimum time on-study of 35 days from the reference start date (reference date is considered Day 1 on study). If the subject is not on-study for at least this amount of time, any tumor assessment indicating stable disease before this time period will have a Best Response of NE unless PD is identified.

Special note on response assessment: When nodal disease is included in the sum of target lesions and the nodes decrease to 'normal' size (< 10 mm), they may still have a measurement reported on scans. This measurement should be recorded even though the nodes are normal in order not to overstate progression should it be based on increase in size of the nodes. As noted earlier, this means that patients with CR may not have a total sum of 'zero' on the case report form (CRF).

Table 2.3.3-1: Best Overall Response (Confirmation of CR and PR Required)

Overall Response First Time Point	Overall Response Subsequent Time Point	Best Overall Response
CR	CR	CR
CR	PR	SD, PD OR PR ^a
CR	SD	SD provided minimum criteria for SD duration met, otherwise, PD
CR	PD	SD provided minimum criteria for SD duration met, otherwise, PD
CR	NE	SD provided minimum criteria for SD duration met, otherwise, NE
PR	CR	PR
PR	PR	PR

Table 2.3.3-1: Best Overall Response (Confirmation of CR and PR Required)

Overall Response First Time Point	Overall Response Subsequent Time Point	Best Overall Response
PR	SD	SD
PR	PD	SD provided minimum criteria for SD duration met, otherwise, PD
PR	NE	SD provided minimum criteria for SD duration met, otherwise, NE
NE	NE	NE

CR = complete response, PR = partial response, SD = stable disease, PD = progressive disease, and
NE = inevaluable

^a If a CR is truly met at first time point, then any disease seen at a subsequent time point, even disease meeting PR criteria relative to baseline, makes the disease PD at that point (since disease must have reappeared after CR). Best response would depend on whether minimum duration for SD was met. However, sometimes 'CR' may be claimed when subsequent scans suggest small lesions were likely still present and in fact the patient had PR, not CR at the first time point. Under these circumstances, the original CR should be changed to PR and the best response is PR.

2.3.4 Confirmation Scans

Verification of Response: To be assigned a status of CR or PR, changes in tumor measurements must be confirmed by consecutive or subsequent repeat assessments that should be performed no less than 28 days after the criteria for response are first met. Subsequent documentation of a CR may provide confirmation of a previously identified CR even with an intervening NE or PR (eg, CR NE CR or CR PR CR). Subsequent documentation of a PR may provide confirmation of a previously identified PR even with an intervening NE or SD (eg, PR NE PR or PR SD PR). However, only one (1) intervening time point will be allowed between PR/CRs for confirmation.

Verification of Progression: Progression of disease should be verified in cases where progression is equivocal. If repeat scans confirm PD, then progression should be declared using the date of the initial scan. If repeat scans do not confirm PD, then the subject is considered to not have progressive disease.

APPENDIX 6 ECOG PERFORMANCE STATUS

ECOG PERFORMANCE STATUS	
0	Fully active, able to carry on all pre-disease performance without restriction
1	Restricted in physically strenuous activity but ambulatory and able to carry out work of a light or sedentary nature, eg, light house work, office work
2	Ambulatory and capable of all selfcare but unable to carry out any work activities. Up and about more than 50% of waking hours
3	Capable of only limited selfcare, confined to bed or chair more than 50% of waking hours
4	Completely disabled. Cannot carry on any selfcare. Totally confined to bed or chair
5	Dead

APPENDIX 7 MANAGEMENT ALGORITHMS

These general guidelines constitute guidance to the Investigator and may be supplemented by discussions with the Medical Monitor representing the Sponsor. The guidance applies to all immuno-oncology agents and regimens.

A general principle is that differential diagnoses should be diligently evaluated according to standard medical practice. Non-inflammatory etiologies should be considered and appropriately treated.

[figure not shown]
Corticosteroids are a primary therapy for immuno-oncology drug-related adverse events. The oral equivalent of the recommended IV doses may be considered for ambulatory patients with low-grade toxicity. The lower bioavailability of oral corticosteroids should be taken into account when switching to the equivalent dose of oral corticosteroids.

Consultation with a medical or surgical specialist, especially prior to an invasive diagnostic or therapeutic procedure, is recommended.

The frequency and severity of the related adverse events covered by these algorithms will depend on the immuno-oncology agent or regimen being used.

GI Adverse Event Management Algorithm

Rule out non-inflammatory causes. If non-inflammatory cause is identified, treat accordingly and continue I-O therapy. Opiates/narcotics may mask symptoms of perforation. Infliximab should not be used in cases of perforation or sepsis.

[figure not shown]

Patients on IV steroids may be switched to an equivalent dose of oral corticosteroids (e.g. prednisone) at start of tapering or earlier, once sustained clinical improvement is observed. Lower bioavailability of oral corticosteroids should be taken into account when switching to the equivalent dose of oral corticosteroids.

Updated 05-Jul-2016

Renal Adverse Event Management Algorithm

Rule out non-inflammatory causes. If non-inflammatory cause, treat accordingly and continue I-O therapy

[figure not shown]

Patients on IV steroids may be switched to an equivalent dose of oral corticosteroids (e.g. prednisone) at start of tapering or earlier, once sustained clinical improvement is observed. Lower bioavailability of oral corticosteroids should be taken into account when switching to the equivalent dose of oral corticosteroids.

Updated 05-Jul-2016

Pulmonary Adverse Event Management Algorithm

Rule out non-inflammatory causes. If non-inflammatory cause, treat accordingly and continue I-O therapy. Evaluate with imaging and pulmonary consultation.

[figure not shown]

Patients on IV steroids may be switched to an equivalent dose of oral corticosteroids (e.g. prednisone) at start of tapering or earlier, once sustained clinical improvement is observed. Lower bioavailability of oral corticosteroids should be taken into account when switching to the equivalent dose of oral corticosteroids.

Updated 05-Jul-2016

Hepatic Adverse Event Management Algorithm

Rule out non-inflammatory causes. If non-inflammatory cause, treat accordingly and continue I-O therapy. Consider imaging for obstruction.

Patients on IV steroids may be switched to an equivalent dose of oral corticosteroids (e.g. prednisone) at start of tapering or earlier, once sustained clinical improvement is observed. Lower bioavailability of oral corticosteroids should be taken into account when switching to the equivalent dose of oral corticosteroids.

[figure not shown]
*I-O therapy may be delayed rather than discontinued if AST/ALT ≤ 8 x ULN or T.bili ≤ 5 x ULN.

**The recommended starting dose for grade 4 hepatitis is 2 mg/kg/day methylprednisolone IV.

Updated 05-Jul-2016

Endocrinopathy Management Algorithm

Rule out non-inflammatory causes. If non-inflammatory cause, treat accordingly and continue I-O therapy. Consider visual field testing, endocrinology consultation, and imaging.

[figure not shown]

Patients on IV steroids may be switched to an equivalent dose of oral corticosteroids (e.g. prednisone) at start of tapering or earlier, once sustained clinical improvement is observed. Lower bioavailability of oral corticosteroids should be taken into account when switching to the equivalent dose of oral corticosteroids.

Updated 05-Jul-2016

Skin Adverse Event Management Algorithm

Rule out non-inflammatory causes. If non-inflammatory cause, treat accordingly and continue I-O therapy.

Patients on IV steroids may be switched to an equivalent dose of oral corticosteroids (e.g. prednisone) at start of tapering or earlier, once sustained clinical improvement is observed. Lower bioavailability of oral corticosteroids should be taken into account when switching to the equivalent dose of oral corticosteroids.

[figure not shown]
*Refer to NCI CTCAE v4 for term-specific grading criteria.

^If SJS/TEN is suspected, withhold I-O therapy and refer patient for specialized care for assessment and treatment. If SJS or TEN is diagnosed, permanently discontinue I-O therapy.

Updated 05-Jul-2016

Neurological Adverse Event Management Algorithm

Rule out non-inflammatory causes. If non-inflammatory cause, treat accordingly and continue I-O therapy.

Patients on IV steroids may be switched to an equivalent dose of oral corticosteroids (e.g. prednisone) at start of tapering or earlier, once sustained clinical improvement is observed. Lower bioavailability of oral corticosteroids should be taken into account when switching to the equivalent dose of oral corticosteroids.

Updated 05-Jul-2016

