7.4.2 Dose Delay due to Toxicity

BMS-986205 and nivolumab administration should be delayed for the following:

- Grade 2 non-skin, drug-related AE, with the exception of fatigue, nausea, vomiting, and anemia
- Grade 2 drug-related creatinine, AST, ALT, and/or total bilirubin abnormalities
- Grade 3 drug-related skin AE
- Grade 3 drug-related fatigue, nausea, vomiting, diarrhea, and anemia
- Grade 3 drug-related laboratory abnormality, with the following exceptions:

- Grade 3 lymphopenia or asymptomatic amylase or lipase elevations do not require dose delay
- Grade ≥ 3 AST, ALT, total bilirubin will require dose discontinuation (see [Section 7.4.4](#))
- Any AE, laboratory abnormality, or intercurrent illness that, in the judgment of the investigator, warrants delaying the dose of study medication (should consult the BMS medical monitor and should be well documented)

In addition, **only BMS-986205** should be delayed for the following:

- Methemoglobin $\geq 15\%$
- Clinically significant elevations in methemoglobin (generally 10% with a normal hemoglobin level⁴²) with any associated Grade 3 AE (hypoxia, dyspnea, confusion, etc.) attributable to sustained elevations of methemoglobin and not attributable to another etiology
- QTcF > 500 msec confirmed by at least 1 repeat ECG and at least 60 msec above baseline (see [Appendix 9](#)).

Participants may continue to receive nivolumab during dose delays of BMS-986205 for elevations of methemoglobin and associated events, as well as QTcF prolongations.

For participants with methemoglobin elevations with associated Grade 3 AEs, if contribution of nivolumab to the associated AE cannot be ruled out (eg, a participant with dyspnea in whom pneumonitis has not yet been ruled out), nivolumab dosing should be delayed as well. See [Section 7.4.6](#) for management of methemoglobinemia.

If BMS-986205 dosing is delayed, dose reduction may be necessary, see [Section 7.4.1](#).

If dosing is resumed after a delay, BMS-986205 may be resumed as soon as the criteria to resume treatment are met (see [Section 7.4.3](#)). Nivolumab should be resumed as soon as possible after criteria to resume treatment are met but may be resumed later than BMS-986205 given the differences in each drug's administration.

Participants who require delay of any study treatment should be re-evaluated weekly or more frequently if clinically indicated and resume dosing when re-treatment criteria are met.

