7.4.3 Criteria to Resume Treatment of BMS-986205 and Nivolumab

Participants may resume treatment with study treatments when the drug-related AE(s) resolve to Grade ≤ 1 or baseline value, with the following exceptions:

- Participants may resume treatment in the presence of Grade 2 fatigue.
- Participants who have not experienced a Grade 3 drug-related skin AE may resume treatment in the presence of Grade 2 skin toxicity.
- For participants with Grade 2 AST, ALT, and/or total bilirubin abnormalities, dosing may resume when laboratory values return to baseline and management with corticosteroids, if needed, is complete.

- Participants with combined AST/ALT AND total bilirubin values meeting discontinuation parameters (Section 7.4.4) should have treatment permanently discontinued.
- Drug-related pulmonary toxicity, diarrhea, or colitis must have resolved to baseline before treatment is resumed. Participants with persistent Grade 1 pneumonitis after completion of a steroid taper over at least 1 month may be eligible for retreatment if discussed with and approved by BMS medical monitor/designee.

Participants with drug-related endocrinopathies adequately controlled with only physiologic hormone replacement may resume treatment after consultation with the BMS medical monitor/designee. Adrenal insufficiency requires discontinuation regardless of control with hormone replacement.

For participants who have BMS-986205 held for elevations of methemoglobin, dosing may resume when the methemoglobin levels have decreased to below the institutional ULN and any associated AEs have resolved to Grade \leq 1 or baseline value. Dose modification of BMS-986205 should be considered when resuming after a delay (see [Section 7.4.1](#)).

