7.4.4 Guidelines for Permanent Discontinuation of BMS-986205 and Nivolumab

BMS-986205 and nivolumab treatment should be permanently discontinued for the following:

- Any occurrence of serotonin syndrome should result in discontinuation of BMS-986205 only.
- Any Grade 2 drug-related uveitis, eye pain, or blurred vision that does not respond to topical therapy and does not improve to Grade 1 severity within the time frame permitted for dose delays OR requires systemic treatment
- Any Grade 3 non-skin, drug-related AE lasting $>$ 7 days or that recurs, with the following exceptions for laboratory abnormalities, drug-related uveitis, pneumonitis, bronchospasm, neurologic toxicity, hypersensitivity reactions, infusion reactions, and endocrinopathies:
 - Grade 3 drug-related uveitis, pneumonitis, bronchospasm, neurological toxicity, hypersensitivity reaction, or infusion reaction of any duration requires discontinuation.
 - Grade 3 drug-related endocrinopathies, adequately controlled with only physiologic hormone replacement do not require discontinuation. Adrenal insufficiency requires discontinuation regardless of control with hormone replacement.
 - Grade 3 drug-related laboratory abnormalities do not require treatment discontinuation except:
 - ◆ Grade 3 drug-related thrombocytopenia lasting 7 days or associated with bleeding requires discontinuation
 - ◆ Grade \geq 3 drug-related AST, ALT, or total bilirubin requires discontinuation*
 - ◆ Concurrent AST or ALT $>$ 3 \times ULN and total bilirubin $>$ 2 \times ULN
 - * In most cases of Grade 3 AST or ALT elevation, study treatment(s) will be permanently discontinued. If the investigator determines a possible favorable benefit/risk ratio that warrants continuation of study treatment(s), a discussion between the investigator and the BMS medical monitor/designee must occur.
- Any Grade 4 drug-related AE or laboratory abnormality (including but not limited to creatinine, AST, ALT, or total bilirubin), except for the following events which do not require discontinuation:

- Grade 4 neutropenia \leq 7 days
- Grade 4 lymphopenia or leukopenia or asymptomatic amylase or lipase
- Isolated Grade 4 electrolyte imbalances/abnormalities that are not associated with clinical sequelae and are corrected with supplementation/appropriate management within 48 hours of their onset

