7.4.5 Management Algorithms for Immuno-Oncology Agents

Immuno-oncology (IO) agents are associated with AEs that can differ in severity and duration from AEs caused by other therapeutic classes. Nivolumab and BMS-986205 are considered IO agents in this protocol. Early recognition and management of AEs associated with IO agents may

mitigate severe toxicity. Management algorithms have been developed from extensive experience with nivolumab to assist investigators in assessing and managing the following groups of AEs:

- gastrointestinal
- renal
- pulmonary
- hepatic
- endocrinopathies
- skin
- neurological

The clinical nature of AEs noted with BMS-986205 will determine the role of the above algorithms for use in toxicities related to its use in this study. The algorithms recommended for utilization in this protocol are included in [Appendix 7](#).

7.4.6 *Management of Treatment-Related Hematological Adverse Events and Detection of Methemoglobinemia*

Symptoms of methemoglobinemia are related to the lack of oxygen delivery to tissues and are proportional to the fraction of methemoglobin, as described below for participants with normal hemoglobin levels.

Symptoms associated with elevations of methemoglobin are as follows:

- 0% to 10% - Usually asymptomatic
- 10% to 20% - Cyanosis without other symptoms
- 20% to 50% - Headache, dyspnea, lightheadedness (possibly syncope), weakness, confusion, palpitations, chest pain
- 50% to 70% - Coma, seizures, arrhythmias; acidosis
- > 70% - Usually death

Note that participants with anemia may experience symptoms at lower methemoglobin percentages than listed above, depending on the degree of anemia.

Increasing levels of methemoglobin may confound the results of standard pulse oximeters, with values of around 85% reported consistently as methemoglobin levels increase, regardless of the true oxygen saturation.

When methemoglobinemia is suspected, part of the diagnostic work-up includes evaluation for other disorders that can present with a similar clinical picture, including cardiac and pulmonary disease. A fresh peripheral blood sample (either venous or arterial) should be sent for evaluation of methemoglobin levels; methemoglobin levels may vary with storage of blood.

For management of methemoglobinemia, see Section 7.4.6. Testing is done at screening and as clinically indicated.

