8 DISCONTINUATION CRITERIA

8.1 Discontinuation from Study Treatment

Participants MUST discontinue IP (and non-IP at the discretion of the investigator) for any of the following reasons:

- Participant's request to stop study treatment. Participants who request to discontinue study treatment will remain in the study and must continue to be followed for protocol specified follow-up procedures. The only exception to this is when a participant specifically withdraws consent for any further contact with him/her or persons previously authorized by participant to provide this information
- Any clinical AE, laboratory abnormality or intercurrent illness which, in the opinion of the investigator, indicates that continued participation in the study is not in the best interest of the participant
- Termination of the study by BMS
- Loss of ability to freely provide consent through imprisonment or involuntarily incarceration for treatment of either a psychiatric or physical (eg, infectious disease) illness
- Inability to comply with protocol
- Discretion of the investigator
- Pregnancy
- Completion of study required procedures
- Documented and confirmed disease progression as defined by RECIST v1.1 (see [Appendix 5](#)) unless participant meets criteria for treatment beyond progression ([Section 8.1.2](#))
- Clinical deterioration while receiving active study therapy that in the opinion of the investigator indicates that continued participation in the study is not in the best interest of the participant
- Protocol-defined reasons for discontinuation (see [Section 7.4.4](#) and [Section 8.2](#))

In the case of pregnancy, the investigator must notify within 24 hours of awareness of the pregnancy, the BMS medical monitor/designee of this event. In the event a female participant becomes pregnant during this clinical trial, the study treatment must be discontinued immediately. In most cases, the study treatment will be permanently discontinued in an appropriate manner (eg, dose tapering if necessary for participant safety). Please call the BMS medical monitor within 24 hours of awareness of the pregnancy. Refer to [Section 9.2.6](#).

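### For a drug-related SJS/TEN case graded below 4, Protocol Appendix 7 says stop permanently while Sections 7.4.2 to 7.4.4 delay and permit resumption, and no order of precedence is stated

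*Protocol*

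**What the plan says.** Protocol Appendix 7, in a footnote to the skin algorithm, gives two steps. On suspicion: "If SJS/TEN is suspected, withhold I-O therapy and refer patient for specialized care for assessment and treatment". On diagnosis: "If SJS or TEN is diagnosed, permanently discontinue I-O therapy". Neither sentence carries a grade condition.

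The appendix describes its own standing in these terms: "These general guidelines constitute guidance to the Investigator and may be supplemented by discussions with the Medical Monitor representing the Sponsor". Section 7.4.5 treats both study drugs as immuno-oncology agents, lists skin among the covered event groups, and links to the appendix with "The algorithms recommended for utilization in this protocol are included in" Appendix 7. It adds that the nature of the events seen with BMS-986205 will decide what part the algorithms play for that drug.

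The dosing rules in the body are written by grade and do not mention SJS or TEN:

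- Section 7.4.2 lists "Grade 3 drug-related skin AE" among the reasons to delay both drugs.
- Section 7.4.3 opens with "Participants may resume treatment with study treatments when the drug-related AE(s) resolve to Grade" 1 or less, or the baseline value. None of its exceptions concerns SJS or TEN.
- Section 7.4.4 sets its Grade 3 stopping rule for "Any Grade 3 non-skin, drug-related AE lasting" more than 7 days or recurring. It also stops treatment for any Grade 4 drug-related event, with no skin event among the exceptions, and for any event that the investigator judges a substantial clinical risk.
- Section 8.1 lists the reasons for which participants must discontinue. One is "Protocol-defined reasons for discontinuation (see" Sections 7.4.4 and 8.2). Appendix 7 is not cited there.

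**The concern.** A site with a diagnosed case has two places to look. The appendix names the diagnosis and says to stop for good. The dosing sections go by grade alone; at Grade 3 they lead to a delay and then to possible resumption. The list that Section 8.1 makes mandatory contains neither the diagnosis nor a Grade 3 skin rule.

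What is at stake is re-exposure to both drugs. An investigator who follows 7.4.2 to 7.4.4 as written may resume treatment after a diagnosis for which the protocol's own appendix says to stop permanently. Two investigators, each following a part of the same protocol, could act differently on the same case.

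**Working it through.** No arithmetic applies: the point rests on no sample size, rate or power figure. The check sets the texts side by side by grade, for a diagnosed SJS or TEN case judged drug-related.

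| Grade of the case | Appendix 7 | Sections 7.4.2 to 7.4.4 | Same action? |
|---|---|---|---|
| 4 | Permanent stop | Permanent stop (7.4.4, any Grade 4 drug-related event; no skin exception) | Yes |
| 3 | Permanent stop | Delay (7.4.2); resumption permitted at Grade 1 or less, or baseline (7.4.3); Grade 3 stopping rule excludes skin (7.4.4) | No, unless a judgment clause is used |
| Below 3, if a case were so graded | Permanent stop | No mandatory delay (the Grade 2 rule in 7.4.2 is for non-skin events); no grade-based stop | No, unless a judgment clause is used |

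The Grade 3 row is the secure one, because every step in it is written out. The last row matters only if such a case is ever graded below 3, and the documents do not say whether that can happen.

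Next, does anything in the protocol settle the Grade 3 row?

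1. *Judgment clauses.* Section 7.4.4 stops treatment for an event that the investigator considers a substantial clinical risk. Section 8.1 does so where the investigator thinks that continuing is not in the participant's best interest. Either can produce the appendix's result, but neither ensures it.
2. *The link in 7.4.5.* It brings the skin algorithm in as recommended, and leaves its role for BMS-986205 toxicity to depend on the kind of events seen. It does not rank the appendix above or below 7.4.2 to 7.4.4.
3. *The mandatory lists.* Section 8.1 points to 7.4.4 and 8.2. The continuation rule in Section 5.1 points to 7.4.4. Neither points to Appendix 7.
4. *How 7.4.4 is built.* Where it wants a stop whatever the duration or control, it names the condition, as with pneumonitis, bronchospasm and adrenal insufficiency. SJS and TEN are not named, and skin is expressly left out of the Grade 3 rule. A reader could take that as meaning no mandatory stop.

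Nothing in the protocol therefore fixes the answer for a Grade 3 case.

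**The case against.** The strongest reply is that the texts can be followed together. Withholding on suspicion and delaying for a Grade 3 skin event are the same first step. Section 7.4.3 only permits resumption, so an investigator who stops under Appendix 7 breaches nothing in 7.4.2 to 7.4.4. Section 7.4.5 already points to the appendix, and a specific instruction can be read as adding to a general one. The appendix also calls itself guidance, so it is too strong to say that it requires anything.

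Much of this stands. A reader might infer that the protocol orders re-treatment of SJS or TEN; no text does. A reader might also infer that every case is in conflict; Grade 4 drug-related cases are not. What remains is that resuming a Grade 3 case also breaches nothing in 7.4.2 to 7.4.4, and the only specific instruction against it sits in guidance that the mandatory list does not cite.

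Two further readings are tempting and do not hold:

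- *That the Cycle 0 gate repeats the problem.* Its rash criterion bars a Grade 3 rash from Cycle 1 only if it fails to improve. But the first criterion in the same list (Protocol 5.1, SAP 2.1) bars Grade 2 or higher immune-related events attributed to BMS-986205, and its examples are not exhaustive. A case judged immune-related could be caught there.
- *That the safety endpoint becomes ambiguous.* SAP 7.1.1 classifies an event as leading to discontinuation or delay by the action recorded on the CRF. The classification follows what was done, so the endpoint definition is unaffected.

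Finally, the algorithm figure is not in the text available for review, so the place where the footnote attaches cannot be seen. That the instruction applies at any grade is read from the sentence itself.

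**Conclusion.** The point holds in a limited form. For a diagnosed, drug-related SJS or TEN case graded 3, Appendix 7 leads to a permanent stop and Sections 7.4.2 to 7.4.4 to a delay with permitted resumption. The same gap would open for a lower grade. Agreement depends on the investigator's judgment, and no order of precedence is stated.

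It is best described as an omission from Section 7.4.4 together with an unstated precedence between Section 7.4 and Appendix 7. It should be corrected because it bears on re-exposure after a severe reaction, although no sample size, endpoint definition or analysis changes.

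Its frequency cannot be estimated: the documents give neither the CTCAE grade of SJS or TEN nor an expected rate. The conclusion assumes that a case can be graded below 4, and that the footnote is not tied to one grade in the figure.

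**What to change.** The sponsor should reconcile Sections 7.4.2, 7.4.3 and 7.4.4 with the SJS/TEN footnote in Appendix 7, so that all four give one consistent instruction for diagnosed SJS or TEN. The protocol should also state whether Section 7.4 or Appendix 7 governs where they differ. Which clinical rule to adopt is for the sponsor and its clinical advisers.

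The cost is amendment wording and the usual approvals. No procedure, visit, data item or analysis has to be added.
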